1.0 BACKGROUND AND RATIONALE

1.1 Disease Background

Currently, ultrasound-guided transversus abdominis plane (UTAP) blocks (regional anesthetic blocks) are being employed for the care of urological surgery patients. Local and regional anesthesia is commonly used throughout surgical fields. However, ultrasound-guidance can be challenging, particularly in larger, obese patients. It is unknown how such techniques compare to laparoscopic-guided blockade, with respect to time to perform, learning curve, and postoperative analgesia. The transversus abdominis plane lies deep within the abdominal wall, potentially allowing for greater ease of access from a laparoscopic approach from within than the ultrasound guided percutaneous approach.

Prior randomized studies have been completed comparing UTAP and Placebo. In 2012 Hosgood et al. compared UTAP and placebo (UTAP w/ saline) in 46 live-donor laparoscopic nephrectomy patients (24 UTAP vs. 22 placebo). Pain control (measured using the 0-10 VAS scale) was greater on post-operative day (POD) 1 in patients receiving UTAP than in controls, 19 (15) vs. 37 (20) (presented as mean (SD)), respectively.¹ A similar randomized study in 2014 compared UTAP and placebo (UTAP w/saline) in 21 hand assisted laparoscopic nephrectomy patients (10 UTAP vs. 11 placebo). The study was initially powered for 50 patients but with decreased accrual secondary to a surgeon taking a leave of absence during the study period. Pain scores were recorded using the 0-10 VAS score. Postoperatively at 24 hours (median (IQR)) UTAP patients demonstrated decreased postoperative pain than placebo patients (1 (0-2) vs. 4 (2-6)) on the VAS score, respectively.²

A larger study, done in 2016, with 80 randomized patients undergoing retroperitoneal laparoscopic urologic surgery compared UTAP (40) and saline UTAP (40). Pain scores were assessed using the 0-100 VAS score scale. On POD1, UTAP group had lower pain scores (mean (SD)) of 8.4 (5.9) vs. placebo 28.3 (12.2).³

The most recent study, done in 2018, examined 100 randomized patients undergoing robotic-assisted laparoscopic prostatectomies. Fifty patients were given UTAP blocks while the others received no block. A Numerical Rating Scale (assumed to range from 0-10 as not otherwise specified) was used to assess pain. Patients receiving the block at 24 hours had better pain control (mean (SD)) (1.8 (0.82) vs. 3.57 (0.64)).⁴

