If the null hypothesis, H_{02} is rejected for a given θ , we will claim that LTAP (the experimental approach) retains more than $\theta \times 100\%$ efficacy of UTAP (the active reference) compared with the placebo, and non-inferiority of LTAP to UTAP will be declared.

With a hierarchical step down closed testing procedure (which can occur when one has two or more endpoints for which demonstration of an effect on each is needed to support regulatory approval), the familywise type I error rate is controlled at the level α as there is only one way to succeed, however, the type II error rate is inflated thereby decreasing the overall power to show success on both endpoints. To account for inflation of the type II error rate, the sample size will be calculated to provide an overall power (to detect both endpoints) of 80% by setting the power for each hypothesis test at 90% ($90\% \times 90\% = 80\%$)⁹ corresponding to $\beta=0.10$.

The statistical methodology for a test problem based on the ratio of (differences in) population means was published by Koch et al. (1998).¹⁰ The null hypothesis H_{02} , referred to above as our second hypothesis, can be rejected, if the lower limit of Fieller's one-sided 100 $(1-\alpha)\%$ confidence interval for the ratio of differences in means is greater than θ . Pigeot et al. (2003) investigated Fieller's confidence interval and derived formulas for power and hence sample size calculation. The R package 'ThreeArmedTrials' developed by Tobias Muetze (2016)¹¹ provides a collection of functions for statistical inference in three-arm trials using the formulas derived by Pigeot et al. for a normally distributed outcome. For a study assessing non-inferiority of an experimental approach compared to an active reference, tools to: determine optimal sample size allocation among groups (UTAP, LTAP, Placebo), compute total (and group) sample size required to detect a particular non-inferiority fraction θ at a particular power and alpha level, as well as analyze the final data set are provided. For a normally distributed endpoint the group means, variances as well as power, alpha, group allocation ratios and non-inferiority fraction θ need to be specified for computation of sample size. It is recommended by Muetze to use estimates of means and variances from a random effects meta-analysis of the historical placebo-controlled trials comparing UTAP to placebo (presented in Section 1.1). Based on meta-analysis of the four

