historical placebo-controlled trials with parameters listed in the table below and discussed in the introduction, the estimated pooled mean pain scores and (total variance) was 3.4 (1.50) in the placebo and 1.49 (1.77) in the UTAP groups. The random effects meta-analysis was conducted with the Comprehensive Meta-Analysis Software Version 3.3.070 (2013).¹²

Study name	Treatment	Mean	SD	Variance	Sample size
Hosgood (2012)	Placebo	3.70	2.00	4.00	22
Aniskevich (2014)	Placebo	4.00	2.30	5.29	11
Qu (2016)	Placebo	2.80	1.20	1.44	40
Fabrizio (2018)	Placebo	3.57	0.64	0.41	50
Random	Placebo	3.40		1.50	
Hosgood (2012)	UTAP	1.90	1.50	2.25	24
Aniskevich (2014)	UTAP	1.50	1.20	1.44	10
Qu (2016)	UTAP	0.84	0.59	0.35	40
Fabrizio (2018)	UTAP	1.80	0.82	0.67	50
Random	UTAP	1.49		1.77	

In accordance with ICH guidelines on statistical principles for clinical trials a type I error rate of 0.025 was used for this sample size calculation. Optimal sample size allocation was determined to follow a 2:2:1 ratio of LTAP:UTAP:Placebo. A total sample size of 235 is required with a 2:2:1 allocation ratio (94 LTAP, 94 UTAP and 47 Placebo) to achieve 90% power to establish non-inferiority of LTAP to UTAP with a fixed fraction of 0.50 (LTAP has to achieve more than 50% of the effect of UTAP compared to placebo to claim as non-inferior) assuming means and variances of 1.49 (1.77), 1.49 (1.77) and 3.40 (1.50) in the LTAP, UTAP and Placebo groups, respectively. This sample size calculation was performed using the PowerRet function of the 'ThreeArmedTrials' package with the following parameters:

```
power_RET(experiment = c(1.49,1.77), reference = c(1.49,1.77), placebo = c(3.4,1.5),Delta = 0.7, sig_level = 0.025, power= 0.9, allocation = c(2,2,1)/5,distribution = "normal")
```

The statistical evaluation will be performed in the first step by a two sample t-test for demonstrating superiority of UTAP over placebo. Group sample sizes of 94 and 47 for UTAP and placebo groups achieve over 99% power to reject the null hypothesis of equal or worse means when the population VAS pain score means (SDs) in the UTAP and Placebo groups are 1.50 (1.33) and 3.4 (1.22), respectively, with a significance level of 0.025 using a one-sided two-sample unequal-variance t-test. The calculation was performed with PASS Version 15.

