θ is pre-specified as the fixed fraction of active reference effect (retention of effect) of 0.50 (LTAP has to achieve more than 50% of the effect of UTAP compared to placebo to claim as non-inferior). The second step will be carried out based on the Fieller’s one-sided 97.5% lower confidence bound for the ratio of $\mu_{LTAP} - \mu_{Placebo}$ and $\mu_{UTAP} - \mu_{Placebo}$. If the lower bound of the confidence interval is greater than 50% then the null hypothesis, H_{02} is rejected (LTAP (the experimental approach) retains more than 50% efficacy of UTAP (the active reference) then non-inferiority of LTAP to UTAP will be declared. The formula for calculating Fieller’s confidence bound is presented in Pigeot et al (2003) and will be implemented using The R package ‘ThreeArmedTrials’ developed by Tobias Muetze (2016).

Analysis of Secondary Endpoints:

The secondary endpoints of 24-hour cumulative post-operative opioid analgesic requirement expressed in morphine equivalent dose (MED), intraoperative time taken to complete the surgical block, total operating room time and surgical time will be summarized using median, 1st and 3rd quartiles and minimum and

maximum values. A Kruskal-Wallis analysis of variance will be used to compare the cumulative MED requirement (time to complete the surgical block, total operating room time and surgical time) among the three intervention groups with all pairwise comparisons made between groups using the Dwass-Steel-Critchlow-Fligner procedure (Dwass 1960; Steel 1960; Critchlow and Fligner 1991).¹⁵⁻¹⁷

The secondary endpoint of antiemetic medication use will be reported as the number and percentage of patients that require antiemetic medication during their hospital stay within each intervention group. A Chi-Square will be used to compare percentages across groups. A log-binomial regression model will be used to estimate and compare the prevalence ratios (PR) and corresponding 95% confidence intervals (CI) for antiemetic medication use among patients in the three intervention groups.

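### The planning variances 1.77 and 1.50 are used as patient-level variances but cannot be derived as such from the plan's own table; the stated 90% power needs restating, though N = 235 is not shown to be too small

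*Combined protocol and SAP*

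**What the plan says.** All of the sample-size material is in section 10.2 of the combined protocol and SAP.

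- **What the software needs:** "For a normally distributed endpoint the group means, variances as well as power, alpha, group allocation ratios" and the retention fraction. For the sources of these, the section cites a recommendation "to use estimates of means and variances from a random effects meta-analysis of the historical placebo-controlled trials comparing UTAP to placebo".
- **What the meta-analysis is said to give:** "the estimated pooled mean pain scores and (total variance) was 3.4 (1.50) in the placebo and 1.49 (1.77) in the UTAP groups". The term total variance is not defined, and no derivation is shown.
- **How the figures are used for non-inferiority:** N = 235 is justified "assuming means and variances of 1.49 (1.77), 1.49 (1.77) and 3.40 (1.50) in the LTAP, UTAP and Placebo groups". The printed call contains "reference = c(1.49,1.77), placebo = c(3.4,1.5),Delta = 0.7".
- **How they are used in step 1:** the superiority test is powered assuming that the population means (SDs) in the "UTAP and Placebo groups are 1.50 (1.33) and 3.4 (1.22), respectively". These SDs are the square roots of 1.77 and 1.50.
- **Retention fraction for the analysis:** section 10.3 has it "pre-specified as the fixed fraction of active reference effect (retention of effect) of 0.50".

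**The concern.** The power formula needs the variance between patients within an arm. Section 10.2 uses 1.77 and 1.50 in that role twice, once as variances and once through their square roots as SDs.

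The section's own table makes 1.77 hard to accept for UTAP. The trial variances are 2.25, 1.44, 0.35 and 0.67, and the last two come from 90 of the 124 UTAP patients. The plan also makes UTAP more variable than placebo. Only the 2018 robotic prostatectomy trial (0.67 against 0.41) has that ordering.

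The UTAP/LTAP variance supplies most of the variance of the non-inferiority contrast: 75% at a retention fraction of 0.50 and 91% at 0.7, with the plan's inputs. At stake is whether the stated power, and the account of where 235 comes from, can be relied on.

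**Working it through.** **Inputs.** From the section 10.2 table, in trial order 2012, 2014, 2016, 2018:

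- UTAP: means 1.90, 1.50, 0.84, 1.80; SDs 1.50, 1.20, 0.59, 0.82; n = 24, 10, 40, 50.
- Placebo: means 3.70, 4.00, 2.80, 3.57; SDs 2.00, 2.30, 1.20, 0.64; n = 22, 11, 40, 50.
- Design: 94/94/47, one-sided 0.025, LTAP assumed equal to UTAP, difference 3.40 − 1.49 = 1.91.

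**1. Reproduce the plan's figure.** The contrast is LTAP − θ·UTAP − (1−θ)·placebo. Its size is (1−θ)·1.91 and its variance is vE/nE + θ²·vR/nR + (1−θ)²·vP/nP. Power comes from the noncentral t with N − 3 df.

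- θ = 0.7: variance 1.77/94 + 0.49·1.77/94 + 0.09·1.50/47 = 0.01883 + 0.00923 + 0.00287 = 0.03093, so SE = 0.1759. Noncentrality 0.573/0.1759 = 3.258; power **90.05%**; smallest N for 90% is **235**. The plan's figure reproduces.
- θ = 0.50: variance 0.01883 + 0.00471 + 0.00798 = 0.03152, so SE = 0.1775. Noncentrality 0.955/0.1775 = 5.379; power **99.97%**; N for 90% is **88** (before rounding to whole groups).

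The printed 235 therefore belongs to 0.7 and not to the 0.50 in the text.

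**2. Meta-analysis (DerSimonian-Laird).** tau² = (Q − 3)/C, where w = n/SD² and C = Σw − Σw²/Σw.

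- UTAP: Q = 46.72, C = 115.55, tau² = 0.378, pooled mean 1.490.
- Placebo: Q = 14.46, C = 57.65, tau² = 0.199, pooled mean 3.395.

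Both pooled means agree with the plan.

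**3. Patient-level variances from the same table.**

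| Rule | UTAP | Placebo |
|---|---|---|
| Inverse-variance-weighted | 0.60 | 0.78 |
| Squared n-weighted SD | 0.82 | 1.47 |
| Pooled within-trial, Σ(n−1)SD²/Σ(n−1) | 111.23/120 = 0.93 | 213.13/119 = 1.79 |
| Random-effects-weighted | 1.11 | 2.00 |
| Simple mean | 1.18 | 2.78 |
| Within-trial + tau² | 1.31 | 1.99 |
| Random-effects-weighted + tau² | 1.48 | 2.20 |
| Simple mean + tau² | 1.56 | 2.98 |
| **Plan** | **1.77** | **1.50** |

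UTAP is below 1.77 in every row. Placebo falls on either side of 1.50 depending on the rule. Every row makes placebo the more variable arm.

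**4. What does match.** The sum over the four trials of (SD²/n + tau²):

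- UTAP: 0.2599 + 4·0.3784 = 1.773.
- Placebo: 0.7069 + 4·0.1988 = 1.502.

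This adds up variances of trial means. It grows with the number of trials and does not estimate a between-patient variance. Two more natural outputs of the meta-analysis do not match: the variance of the pooled mean is 0.109 and 0.076, and the average of (SD²/n + tau²) is 0.44 and 0.38 (UTAP, placebo).

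**5. Effect on N and power** (difference 1.91):

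| Variances | N for 90%, θ 0.50 | Power at 235 | N for 90%, θ 0.7 | Power at 235 |
|---|---|---|---|---|
| Plan | 88 | 99.97% | 235 | 90.05% |
| Inverse-variance-weighted | 35 | >99.9% | 85 | >99.9% |
| Within-trial | 62 | >99.9% | 139 | 98.9% |
| Within-trial + tau² | 78 | 99.99% | 187 | 95.4% |
| Random-effects-weighted | 71 | >99.9% | 163 | 97.4% |
| Random-effects-weighted + tau² | 88 | 99.97% | 211 | 92.9% |
| Simple mean | 85 | 99.98% | 183 | 95.8% |
| Simple mean + tau² | 101 | 99.87% | 231 | 90.6% |
| 2012 trial alone | 141 | 98.8% | 328 | 78.3% |
| 2014 trial alone | 130 | 99.2% | 250 | 88.2% |

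The 2016 and 2018 trials' variances give over 99.9% at both fractions. With their own differences in means, the 2012 trial (1.8) gives 97.7% at 0.50 and 73.4% at 0.7, and the 2014 trial (2.5) gives 99.99% and 98.4%.

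**6. Step 1.** With the plan's inputs, SE = √(1.77/94 + 1.50/47) = 0.225 for a difference of 1.9, so power exceeds 99%. With the largest single-trial variances (2.25 and 5.29), SE = √(2.25/94 + 5.29/47) = 0.369. Then 1.9/0.369 − 1.96 = 3.18, and power is still above 99%.

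**The case against.** The strongest reply is that nothing in the trial changes. At the prespecified 0.50, power at 235 is 99.97% with the plan's variances and at least 99.8% with every pooled or averaged alternative. The material error in the stated 90% is then the 0.7 in the call, which moves N from 88 to 235; replacing the variances at 0.50 moves N only within 35 to 101. This stands. The variances are not the main reason why the 90% is wrong, and the two points belong in one edit. It does not make the variances right: a rerun at a reconciled fraction would carry them forward.

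A second reply is that the sum in step 4 is a conjecture. That also stands. The documents do not define total variance. The match uses the table's rounded 2016 placebo entry (2.80, 1.20). Section 1.1 reports that the "UTAP group had lower pain scores (mean (SD)) of 8.4 (5.9) vs. placebo 28.3 (12.2") on a 0–100 scale; with 2.83 (1.22) the placebo sum is 1.42. The finding does not depend on this route, because the values are underived and unmatched without it.

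A third reply is that the placebo figure is near one rule: the squared n-weighted SD gives 1.47. True, but the same rule gives 0.82 for UTAP. The UTAP value is the firm part of the finding.

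A reader might infer from a wrong variance that the trial is underpowered. The documents do not support this. Power falls below 90% only at 0.7 and only with the variances of the 2012 trial (24 and 22 patients) or the 2014 trial (10 and 11 patients, reported in section 1.1 as medians and IQRs). A reader might equally infer that the plan's inputs are safely conservative. That holds against all the pooled inputs in the table at 0.7, but not at 0.50, where the simple mean plus tau² needs 101 against 88.

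**Conclusion.** The point holds and should be corrected. The values 1.77 and 1.50 are used as between-patient variances, and no single patient-level rule checked gives both. The UTAP value exceeds every pooled result, and the ordering of the arms is reversed. The stated 90% at 235 is not the power that the historical patient data imply: at 0.50 that power is at least 99.8% with pooled or averaged inputs and at least 98.8% with any single trial's variances at a difference of 1.91. At 0.7 it is 90.6% or more with pooled or averaged inputs, and 78.3% and 88.2% with the 2012 and 2014 variances.

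These results assume normal scores, LTAP equal to UTAP in mean and variance, full 94/94/47 enrolment and the historical trials as tabulated. The ranges cover the listed rules only. The adequacy of 235, the type I error rate, the tests and the Fieller analysis are not called into question.

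**What to change.** In section 10.2:

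1. Replace 1.77 and 1.50 with derived patient-level variances per arm and name the pooling rule, for example pooled within-trial 0.93 and 1.79, or 1.31 and 1.99 with tau². The choice is for the sponsor's statistician.
2. Reconcile the retention fraction between the text, the printed call and section 10.3.
3. Rerun the non-inferiority and step 1 calculations at the fraction that the analysis will use.
4. Restate power at 235 with a sensitivity range, labelling each entry by pooling rule and difference in means.
5. Keep N at 235, but describe it as a fixed size with its recomputed power and not as the number required for 90%. Otherwise the example variances, which need 62 at 0.50, would leave 235 without a stated rationale.

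The cost is two reruns and one rewritten paragraph. Enrolment, allocation, alpha and the analysis methods are unchanged.

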Objectives	
Primary Objectives
 
 To verify assay sensitivity by demonstrating that UTAP (the active reference) is superior than local bupivacaine at controlling 24 hour postoperative pain. To demonstrate non-inferiority of LTAP (the experimental approach) to UTAP (the active reference) with respect to 24 hour postoperative pain control. 
Secondary Objectives
 
 To determine the efficacy of regional blocks on postoperative pain control. To determine whether the LTAP ability of regional blocks to reduces narcotic 24 hour cumulative postoperative opioid analgesic requirement usage in the perioperative period compared to UTAP and Placebo. To determine the rate of antiemetic medication use during postoperative course in UTAP, LTAP, and Placebo groups. To determine the days to return of bowel function in the UTAP, LTAP, and Placebo groups. To determine the length of hospital stay in the UTAP, LTAP and Placebo groups. To determine the time taken to complete the surgical block, operating room time, and surgical time in the UTAP, LTAP and Placebo groups. To determine whether determine the efficacy of LTAP is non-inferior to UTAP ultrasound and laparoscopic regional blocks in obese patients. To determine procedure related complications and adverse events including bleeding or injection of anesthetic intravascular 	
Number of Subjects	235 (94 LTAP, 94 UTAP, 47 Placebo)	
Diagnosis and Main Inclusion Criteria	Robotic Prostatectomy and Partial nephrectomy patients	
Study Product(s), Dose, Route, Regimen	None	

Duration of administration	None
Reference therapy	None
Statistical Methodology	

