4.8 Patient Replacement

If any patient expires, is converted to open surgery, or requires a return to the operating room they will be removed from the study.

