10.3 Data Analyses Plans

Analysis of Co-Primary Endpoints:

The distribution of VAS pain scores in each group will be examined and assessed for normality and homoscedasticity, visually, by generating probability-probability (P-P) plots, boxplots, stem-and-leaf plots and quantile-quantile (Q-Q) plots, and with the Shapiro-Wilk normality test. If necessary, a transformation of the data will be made to render appropriate for parametric testing. All analyses will be performed on patients who undergo surgery and have a 24 hour VAS pain score assessment. Balance on baseline characteristics (including gender, age at surgery, height, weight, BMI, and operative time) among the randomized groups will be assessed separately for each intervention, using the standardized difference. Any variable with an absolute standardized difference >0.52 (i.e., $1.96 \times 1/n_1 + 1/n_2$) for either intervention will be adjusted for in secondary analyses.^{13,14}

A step-down hierarchical hypothesis testing approach will be used to test the two hypotheses (co-primary endpoints). In the first step, to establish assay sensitivity, the alternative hypothesis that the 24-hour post-operative mean VAS pain score in the UTAP group is superior to that in the placebo group will be tested by a one-sided two sample t-test at the 0.025 level of significance ($H_{01}: \mu_{UTAP} \geq \mu_{Placebo}$ vs. $H_{A1}: \mu_{UTAP} < \mu_{Placebo}$).

If assay sensitivity is demonstrated in the first step by rejecting the null hypothesis, H_{01} , we will proceed to the second step of testing for non-inferiority of LTAP to UTAP. To establish non-inferiority, the alternative hypothesis that LTAP is non-inferior to UTAP will be tested using the ‘fractional approach’ introduced by Pigeot et al (2003) where the effect estimate is based on the ratio of the differences in means between LTAP and placebo and UTAP and placebo ($H_{02}: \frac{\mu_{LTAP} - \mu_{Placebo}}{\mu_{UTAP} - \mu_{Placebo}} \leq \theta$: vs. $H_{A2}: \frac{\mu_{LTAP} - \mu_{Placebo}}{\mu_{UTAP} - \mu_{Placebo}} > \theta$).

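### The 90% power stated in 10.2 is not the power of 235 enrolled patients under the plan's own removal and analysis rules: slightly too high at the printed Delta = 0.7, far too low at the stated fraction of 0.50

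*Combined protocol and SAP*

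**What the plan says.** Section 10.2 presents 235 as the number that the calculation requires: "A total sample size of 235 is required with a 2:2:1 allocation ratio (94 LTAP, 94 UTAP and 47 Placebo) to achieve 90% power". The synopsis, under Number of Subjects, repeats it as "235 (94 LTAP, 94 UTAP, 47 Placebo"), and the study schema shows the same three group sizes. No section gives a loss rate or an allowance for losses.

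Four other places bear on how many of those patients reach the analysis:

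- 10.1 reveals the assignment once a patient has been screened and has consented, so randomisation does not wait for the outcome of surgery.
- 4.8 states: "If any patient expires, is converted to open surgery, or requires a return to the operating room they will be removed from the study". The section is headed Patient Replacement but describes no replacement. Conversion to open surgery is also listed as an exclusion criterion (3.2.2).
- 5.5 lets patients leave at any time at their own request, or be withdrawn by the investigator.
- 10.3 defines the analysis set: "All analyses will be performed on patients who undergo surgery and have a 24 hour VAS pain score assessment".

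Section 10.2 also gives two retention fractions. The sentence claims the sample size is enough "to achieve 90% power to establish non-inferiority of LTAP to UTAP with a fixed fraction of 0.50". The printed software call has "Delta = 0.7, sig_level = 0.025, power= 0.9, allocation = c(2,2,1)/5". The decision rule in 10.3 uses 0.50.

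**The concern.** A sample size formula of this kind returns the number of patients with a usable outcome. Here the same number serves as the number of subjects, while the plan's own rules can only make the analysed number smaller. A reader will take 90% as the power of the trial as enrolled. If 235 leaves no slack, that figure describes a trial in which nobody is removed, withdraws or misses the 24-hour score.

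What is at stake is the accuracy of a stated operating characteristic of the non-inferiority test. Whether the error matters depends on which of the two retention fractions is meant.

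**Working it through.** **Inputs, all from 10.2 unless noted.** Means (variances): LTAP 1.49 (1.77), UTAP 1.49 (1.77), placebo 3.40 (1.50). Allocation 2:2:1, so 94, 94 and 47. For the error rate, 10.2 says "a type I error rate of 0.025 was used for this sample size calculation", and 10.3 applies a "Fieller’s one-sided 97.5% lower confidence bound"; the test is therefore one-sided at 0.025. Retention fraction D: 0.7 in the call, 0.50 in the sentence and in 10.3. Loss rates are my assumption, equal across arms.

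**Formula.** With equal means for LTAP and UTAP, the effect is (1 − D) × (3.40 − 1.49) = (1 − D) × 1.91. The variance is 1.77/n_LTAP + D² × 1.77/n_UTAP + (1 − D)² × 1.50/n_placebo. Power is computed by normal approximation, Φ(effect/SE − 1.96), and by noncentral t with Satterthwaite degrees of freedom.

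**Reproducing 235 at D = 0.7.**

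- Effect = 0.3 × 1.91 = 0.573.
- Variance = 0.01883 + 0.00923 + 0.00287 = 0.03093; SE = 0.1759; effect/SE = 3.258.
- Normal approximation: Φ(3.258 − 1.960) = 90.3%. The N for 90% is (1.960 + 1.282)² × (1.77/0.4 + 0.49 × 1.77/0.4 + 0.09 × 1.50/0.2) / 0.573² = 232.6, so 233.
- Noncentral t: 90.01% at 235 and 89.89% at 234. So 235 is the exact minimum, and it reproduces the plan's figure.

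**The same at D = 0.50.**

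- Effect = 0.5 × 1.91 = 0.955.
- Variance = 0.01883 + 0.00471 + 0.00798 = 0.03152; SE = 0.1775; effect/SE = 5.379.
- Power at 235 is 99.97% by either method. The N for 90% is 86 (normal) or 88 (t). The fraction named in the sentence therefore does not give 235.

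**Step 2 power after losses (t-based), group sizes multiplied by (1 − loss).**

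| Assumed loss | Analysed N | D = 0.7 | D = 0.50 |
|---|---|---|---|
| 0% | 235 | 90.0% | 99.97% |
| 2% | 230.3 | 89.4% | 99.96% |
| 5% | 223.3 | 88.5% | 99.94% |
| 10% | 211.5 | 86.7% | 99.91% |
| 15% | 199.8 | 84.8% | 99.85% |
| 20% | 188.0 | 82.5% | 99.76% |
| 25% | 176.3 | 80.0% | 99.62% |

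At D = 0.50, power is still 96.4% at 50% loss and falls to 90% only at about 62% loss.

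**Overall power.** Section 10.2 aims for 80% across both steps, with 90% for each. For step 1 the plan's SDs of 1.33 and 1.22 and a difference of 3.4 − 1.50 = 1.9 give SE = √(1.33²/94 + 1.22²/47) = 0.2247 and power above 99.9%. At 50% loss it is still above 99.9%. Overall power is therefore practically the step 2 power, and at D = 0.7 it stays at or above 80% up to about 25% loss.

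**The case against.** The strongest case against the point is that it has no consequence for the trial as specified. The sentence in 10.2 and the rule in 10.3 both use 0.50, where losing more than half the patients would still leave 90% power. Even at 0.7, which appears only in the printed call, the plan's own criterion is 80% overall, and plausible losses do not breach it. Large losses are also unlikely. The endpoint is at 24 hours, patients are followed as inpatients (4.6), and the pain scale is part of standard postoperative care (7.1.2). Finally, the synopsis speaks only of the number of subjects, and 4.8 carries a heading about replacement, so 235 might be meant as the analysable number.

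Most of this stands, and it sets the limits of the point. A reader might infer that the trial keeps 90% power only if almost nobody is lost. The documents do not support that in general: it is true at 0.7 and false at 0.50. A reader might also infer that the trial is underpowered or must enrol more patients. That does not follow at either fraction, given the 80% target. Nor is this an arithmetic slip in deriving 235, which the printed call reproduces exactly.

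What the objection does not remove is that the printed 90% is wrong at both fractions. At 0.7 it is the power of 235 analysed patients, with no slack. At 0.50 it is not the power of 235 patients at all. The uncertainty about replacement is itself a gap to close, because the text of 4.8 does not say what its heading suggests.

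**Conclusion.** The point holds in a limited form, as a minor reporting defect. Under neither fraction is 90% the power of 235 enrolled patients given the removal rules and the analysis set.

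- At Delta = 0.7 the figure is slightly optimistic: 1.5 points at 5% loss, 3.3 at 10% and 5.2 at 15%.
- At 0.50 it is about 10 points too low, and losses do not matter in practice.

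These figures rest on the plan's own means and variances, on losses spread equally over the arms, and on loss rates that I assumed because the documents give none. They describe loss of precision only. Whether leaving out randomised patients could bias the comparison is a separate question that this calculation does not address.

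**What to change.** In this order, in 10.2:

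1. Reconcile the retention fraction, so that the sentence, the printed call and the decision rule in 10.3 agree.
2. State whether 235 is the enrolled or the analysable number, and whether patients removed under 4.8 are replaced. Reconcile 4.8 with 10.3, which leave open whether a patient converted to open surgery who has a 24-hour VAS is analysed; the expected analysed number depends on this.
3. Give the expected number of patients with surgery and a 24-hour VAS, with the loss rate assumed.
4. Restate the power for that number at the reconciled fraction. If 235 is the enrolled number and 5–10% are lost without replacement, this is about 87–88% at 0.7 or above 99.9% at 0.50.

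The cost is a few sentences and one restated figure, which is slightly less favourable at 0.7 and more favourable at 0.50. No extra enrolment is needed.
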